It provides information about procedures for entering participants into the trial, and provides sufficient detail to enable: an understanding of the background, rationale, objectives, trial population, intervention, methods, statistical analyses, ethical considerations, dissemination plans and administration of the trial; replication of key aspects of trial methods and conduct; and appraisal of the trial's scientific and ethical rigour from the time of ethics approval through to dissemination of the results. The protocol should not be used as an aide-memoire or guide for the treatment of other patients. Every care has been taken in drafting this protocol, but corrections or amendments may be necessary. These will be circulated to registered investigators in the trial. Sites entering participants for the first time should confirm they have the correct version through a member of the trial team at NCTU.

NCTU supports the commitment that its trials adhere to the SPIRIT guidelines. As such, the protocol template includes the Standard Protocol Items: Recommendations for Interventional Trials (SPIRIT) 2012 Statement for protocols of clinical trials (Chan et al 2013). The SPIRIT Statement Explanation and Elaboration document can be referred to, or a member of NCTU Protocol Review Committee can be contacted for further detail about specific items.

1.1 Compliance

The trial will be conducted in compliance with the approved protocol, the Declaration of Helsinki (2008), the principles of Good Clinical Practice (GCP), the UK Data Protection Act and General Data Protection Regulation (GDPR), and the National Health Service (NHS) Research Governance Framework for Health and Social Care (RGF). Agreements that include detailed roles and responsibilities will be in place between participating sites and NCTU.

Participating sites will inform NCTU as soon as they are aware of a possible serious breach of compliance, so that NCTU can fulfil its requirement to report the breach if necessary within the Sponsors timelines specified in the UK Clinical Trials Regulations (currently 7 days). For the purposes of this regulation a 'serious breach' is one that is likely to affect to a significant degree:

- The safety or physical or mental integrity of the subjects in the trial, or
- The scientific value of the trial.

1.2 Sponsor

Norfolk and Norwich University Hospitals NHS Foundation Trust is the trial sponsor and has delegated the overall management of the PREPARE-ABC trial jointly to the Co-Cls and NCTU. Queries relating to sponsorship of this trial should be addressed to the Co-Cls, Director, NCTU, or via the trial team.

1.3 Structured trial summary

Primary Registry and Trial	ISRCTN82233115
Identifying Number	13/10/10/22/33113
Date of Registration in Primary	07/07/2016
Registry	07/07/2010
Secondary Identifying Numbers	NIHR HTA 14/192/53
Secondary identifying Numbers	NNUH Ref Number: 200804
	REN Number: R200647
	NU Ref: RPJ01780
Source of Monetary or Material	This trial is funded by NIHR Health Technology Assessment
Support	Programme
Sponsor	Norfolk and Norwich University Hospitals NHS Foundation
Sportsor	Trust
Contact for Public Queries	[contact]
Contact for Clinical Queries	[name]
Contact for Chilical Queries	[contact]
	[name]
	Consultant General and Colorectal Surgeon
	General Surgery
	Norfolk and Norwich University Hospitals NHS Foundation
	Trust
	[name]
Contact for Information on the	[name]
Exercise Interventions	[contact]
Lacroise interventions	[name]
	Head, Department of Sport, Exercise and Rehabilitation
	Faculty of Health and Life Sciences
	[name]
	Northumbria University
	[name]
Public Title	SupPoRtive Exercise Programmes for Accelerating REcovery
	after major ABdominal Cancer surgery (PREPARE-ABC)
Scientific Title	SupPoRtive Exercise Programmes for Accelerating REcovery
	after major ABdominal Cancer surgery (PREPARE-ABC) –
	A multicentre, 3 arm, parallel randomised controlled trial of
	standard care alone versus standard care plus supervised
	hospital based exercise and standard care plus supported
	home-based exercise pre and post hospital discharge in
	cancer patients awaiting curative colorectal cancer surgery.
Countries of Recruitment	United Kingdom and Ireland
Health Condition(s) or Problem(s)	Post-operative recovery in patients awaiting curative
Studied	colorectal cancer surgery.
Intervention(s)	Arm A
	Hospital-Based Supervised exercise programme consisting
	of:
	Pre-surgery:
	Initial 45 minute exercise counselling incorporating
	behaviour modification techniques.
	Patients will be offered three sessions per week of aerobic
	interval exercise on a cycle ergometer over 3-4 weeks prior
	to their procedure (aim is to achieve 12 sessions). In

addition, patients will undertake twice weekly resistance exercise. Exercise programmes will be tailored to each patient, taking previous level of activity, mobility and any barriers to exercise into consideration.

Post-surgery:

6 weeks post-surgery to 12 months post-randomisation: Patients will be encouraged to comply with current physical activity recommendations: 150 minutes of moderate intensity aerobic exercise per week (brisk walking / cycling) and two sessions of resistance exercise per week. They will also be sign posted to local exercise facilities and receive monthly supervised 'booster' exercise sessions.

Arm B

Home-Based Supported exercise

Pre-surgery:

Initial 45 minute exercise counselling incorporating behaviour modification techniques. Patients will then be encouraged to comply with current physical activity recommendations, which will form the basis of the home exercise programme: a minimum of 150 minutes of moderate intensity aerobic exercise per week (brisk walking / cycling) and two sessions of resistance exercise. Exercise programmes will be tailored to each patient, taking previous level of activity, mobility and any barriers to exercise into consideration. Patients will receive weekly 15 minute telephone support from a member of the Trial Intervention Team to encourage compliance with the exercise programme.

Post-surgery:

6 weeks post-surgery to 12 months post-randomisation: Patients will be encouraged to comply with current physical activity recommendations and sign posted to local exercise facilities and receive monthly 15 minute motivational telephone calls from a member of the Trial Intervention Team.

Arm C

Standard care/Treatment as Usual Treatment as Usual (TAU) comprising the patient information leaflet only. No other information relating to peri-operative exercise will be offered, consistent with current practice.

Key Inclusion and Exclusion Criteria

Target population: NHS patients awaiting a curative elective colorectal resection for cancer.

Inclusion Criteria:

- 1. Male and female participants ≥ 18 years old
- Awaiting a curative elective colorectal resection for cancer

	 American Society of Anaesthesiologists physical status I-III (ASA, 2014)
	4. Able and willing to provide informed consent
	Able and willing to provide informed consent Understand verbal and written instructions in
	5. Understand verbal and written instructions in English
	6. Patients who are already participating (or have
	participated) in other trials may be eligible, but this
	must be agreed in advance by the relevant trial
	teams. Trials where there is already an agreement
	in place, are listed in section 5.3.1.4
	Exclusion Criteria:
	1. Contra-indications to exercise (e.g. lower limb
	amputation without prosthesis, bone, joint or
	muscle problem which may be exacerbated by
	exercise, chronic lung disease causing desaturation
	with exercise or shortness of breath at rest, severe
	psychiatric health problems)
	2. Cardiovascular contra-indications (e.g. unstable
	angina, acute left ventricular failure, uncontrolled
	cardiac arrhythmias, uncontrolled hypertension,
	cardiac event in the previous 6 weeks, cerebral
	vascular disease resulting in transient ischaemic
	attacks)
	3. Participation in other treatment trials, where this
	has not been agreed in advance with both trial
	teams.
Study Type	A multi-centre, single blind (assessors only), 3-arm
	randomised controlled trial recruiting cancer patients
	awaiting curative colorectal cancer surgery from colorectal
Data of First Foundation	units in the UK and Ireland
Date of First Enrolment Target Sample Size	1 November 2016 1146 patients
Primary Outcome(s)	Two primary outcomes will be used:
Trimary Gateome(s)	Two primary outcomes will be used.
	Short term outcome:
	Morbidity for standard care versus hospital based and
	standard care versus home based exercise interventions
	(both exercise interventions are in addition to treatment as
	usual). Assessed by Clavien-Dindo classification of post-
	operative complications
	Measured 30 days post-operatively
	Long Term Outcome:
	Health-related quality of life at 12 months for standard care
	versus hospital based and standard versus home based
	exercise interventions. Assessed by the Medical Outcomes
	Study Short-Form Health Questionnaire (SF-36) 12 months
	post-randomisation.

Key Secondary Outcomes

The following secondary outcomes will be assessed for standard care versus hospital based and standard care versus home based exercise interventions:

Pre-operative outcomes

The following outcomes will evaluate response to the intervention in the pre-operative phase of the study only.

Outcome: Pre-operative change in cardiopulmonary exercise test (CPET).

Metric: Change in cardiopulmonary fitness variables, as measured using an incremental CPET between 4 weeks prior to surgery and shortly before surgery (e.g. peak VO2; anaerobic/ventilatory threshold; VE/VCO2; oxygen pulse).

Outcome: Pre-operative change in grip strength.

Metric: Change in grip strength as measured using a standard digital grip strength dynamometer

Post-operative outcomes:

Outcome: Length of hospital stay

Metric: Duration of stay from date of operation to discharge immediately following operation

Outcome: Fitness for discharge

Metric: Patients will be considered fit for discharge if they meet the following criteria: oral intake established to meet nutritional needs; independence (or return to previous level of function) in washing, dressing and mobility; post-operative pain control met with oral analgesia; passing flatus. Clinical teams managing the patient's post-operative care and blinded to treatment intervention will be responsible for assessing fitness for discharge.

Outcome: Morbidity at discharge

IRAS No: 200804

Metric: Measured by Clavien-Dindo classification of postoperative complications, assessed by the clinical / research team who are blinded to the treatment intervention.

Outcome: 90-day all cause re-admission rate Metric: 90-day all cause re-admission will be recorded by the local research teams, from date of operation.

Outcome: 90-day post-operative mortality, Metric: Defined as percentage of patients who died on or up to 90 days following date of operation.

Outcome: Post-operative change in grip strength.

Metric: Change in grip strength as measured using a standard digital grip strength dynamometer

The following outcomes will be evaluated at baseline, 6 months and 12 months post-randomisation:

Outcome: Physical activity behaviour

Metric: Measured using modified Godin Leisure Time

Exercise Questionnaire (modified)

Outcome: Psychological health status,

Metrics: Measured using Hospital Anxiety and Depression

Scale (HADS)

Outcome: Self-efficacy and motivation for exercise, Metric: Measured using four brief questionnaires: Self-Efficacy for Exercise scale, Behavioural Regulation in Exercise Questionnaire (BREQ-3), Exercise Identity Scale (EIS)

Outcomes: cost effectiveness and quality of life Metric: Patient reported health resource use costs

Hospital reported costs

Metric: Health related Quality of Life (HRQoL) as reported

using EuroQol EQ5D-5L

1.4 Roles and responsibilities

These membership lists are correct at the time of writing; please see terms of reference documentation in the TMF for current lists.

TMT	Trial Management Team					
ToR	Terms of Reference					
TSC	Trial Steering Committee					
UEA	University of East Anglia					
UoN	University of Nottingham					
	•					

4 Introduction

4.1 Background and Rationale

Colorectal cancer is the fourth commonest cancer in the UK with 40,000 patients diagnosed per year (CRUK, 2015). The current standard, and best-proven, treatment for this patient group is a surgical resection with approximately 25,000 patients in the UK undergoing a major abdominal resection each year. A colorectal resection, while offering the best chance of cancer survival, results in significant post-operative mortality (3-5%) (ACPGBI, 2014) and reduced quality of life (Santa Mina et al, 2014).

Post–Operative Morbidities (POMs) following major abdominal surgery place a significant psychological and health burden on patients, while impacting greatly on available healthcare resources. The increased utilization of healthcare is evident in both primary and secondary care. POM results in a significant elevation in the required level of inpatient care, with extended stays in the intensive care unit, the need for multiple returns to theatre for re-operation, increased radiological interventions and an increase in the average length of hospital stay from 5-7 days, to weeks and months. Post-discharge, patients have increased rates of post-discharge re-admission to hospital and require greater input from district and community stoma care nurses and primary care physicians.

Complication rates within the reported literature vary as a function of patient selection within studies, time/intensity of follow up, and definition of complication. Grocott et al (2007) showed that in patients undergoing major abdominal surgery, 78% have a POM / complication at day 5 with 50% continuing at day 8. They indicate that morbidity at or beyond day 5 results in longer post-operative stays and increased resource utilisation. A review of 1200 gastrointestinal procedures (389 colorectal) to determine the cost burden of complications in the US demonstrated a complication rate of 53.8% at day 30 (Vonlanthen et al., 2011). The most recently reported UK colorectal trial of patients undergoing open vs. laparoscopic resectional colorectal surgery - EnROL (Kennedy et al., 2014) reported a total complication rate of 34%. This lower complication rate may be attributable to differences in the severity of the study population as EnROL required patients to be suitable for laparoscopic surgery. The 2014 National Bowel Cancer Audit (NBOCA, 2014) indicates that in England and Wales only 50% of elective colorectal resections are performed laparoscopically. It is therefore likely that the complication rate in EnROL may not be equally comparable to an unselected group of patients undergoing a colorectal resection. A recent small scale feasibility study comprising of a 3 month consecutive review of patients (98 elective) undergoing a colorectal resection (either open or laparoscopic) demonstrated that 55% of elective patients had a significant POM within 30 days.

Post-surgical complications significantly increase the cost of patient care and have marked financial implication to the NHS, in some cases costing five times as much, where complications lead to POMs, compared to patients undergoing a similar operation with no complications (Vonlanthen et al., 2011). Individual patient level costing provided by the NNUH places the average cost of a colorectal resection at £7,500. Estimates suggest that a post-surgical complication could conservatively double the cost of post-operative care. Therefore interventions to reduce post-surgical complications could provide significant cost-savings to the NHS.

Considerable research has focussed on improving post-surgical outcomes. The Improving Surgical Outcomes Group reported a correlation between the level of cardiopulmonary fitness and post-operative clinical outcomes (ISOG, 2005). This suggests that maximising pre-operative cardiopulmonary fitness could improve post-surgical outcomes. Systematic review evidence suggests that exercise training can improve Prepare-ABC Protocol

cardiopulmonary fitness in the short period available prior to surgery (Santa Mina et al., 2014, Singh et al., 2013) and can reduce the risk of post-operative complications following major cardiac and abdominal surgery (Valkenet, 2011). However, most studies to date have been of low to moderate quality and more robust definitive randomized controlled trials are needed.

The Anaesthesia and Perioperative Care Priority Setting Partnership (May 2015), a collaborative involving patients, the public and clinical professionals, identified 'How can pre-operative exercise or fitness training, including physiotherapy, improve outcomes after surgery' as one of the top 10 priorities for peri-operative care research (NIAA, 2015).

The health benefits of physical activity for cancer patients are recognized by the National Cancer Survivor Initiative (NCSI), a partnership between NHS England and Macmillan Cancer Support (NCSI, 2014). The NCSI places the promotion of post-operative physical activity as one of its four main pillars in the rehabilitation of cancer patients. However lifestyle / exercise advice is not yet routinely given to cancer patients. This is, in the main, due to reluctance of health professionals to discuss lifestyle factors with cancer patients due to limitations in knowledge and an inadequacy in the available evidence (Miles et al., 2010).

The role of pre-operative exercise 'prehabilitation' in improving pre-operative cardiopulmonary fitness and its impact on surgical outcomes remain poorly defined, as does the effectiveness of different exercise delivery methods (e.g. hospital-based supervised programmes vs. supported home-based exercised programmes). While self-directed home-based exercise can be delivered in a more cost effective manner, a more intensive exercise intervention (hospital-based supervised) may be required to evoke the clinically meaningful changes required to impact on post-operative morbidity and HR QoL. (Unpublished pilot study REC: 13/EE/0319, IRAS Project ID 129902)

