Cardiopulmonary exercise testing (CPET) will be used as an objective method of evaluating oxygen transport and utilization during a dynamic exercise challenge and it reflects the ability of the cardiopulmonary system to deliver oxygen to the tissues under conditions of stress. Evidence from systematic reviews and more recent studies suggests that CPET variables can reliably predict patients at increased risk of post-operative complications and morbidity following major surgery for abdominal cancers, aortic aneurysm repair, thoracic surgery and colonic surgery (Benzo et al., 2007, Smith et al., 2009, Thompson et al., 2011, West et al., 2013).

Small-scale feasibility studies have reported improvements in functional outcomes following supported home-based aerobic exercise in conjunction with progressive resistance exercise in cancer patients before surgery (Timmerman et al., 2011, Carli et al., 2010, Li et al., 2013). There is also evidence that such programmes can be successfully continued soon after major cancer surgery (Li et al., 2013, Gillis et al., 2012) and patients who engaged in structured exercise programmes before and after their operation had significantly better functional capacity up to 8 weeks post-surgery (Li et al., 2013). A recent prospective study using similar methodology, pre-operative aerobic interval training, delivered as a hospital based intervention for colorectal cancer patients following post-chemoradiotherapy demonstrated changes in physical fitness following a short programme (6 weeks) of exercise and reported over 90% compliance (West et al., 2015).

The potential role of post-operative exercise programmes for helping to optimise long-term recovery after major abdominal cancer surgery has also been recognized. Preliminary evidence suggests that pre-operative exercise promotes better adherence to post-operative exercise (Gillis et al., 2012) and epidemiological data shows that a physically active lifestyle after curative colorectal cancer treatment enhances survival (Meyerhardt et al., 2006).

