5.4 Interventions

There are three trial arms:

- Arm A Hospital based supervised exercise
- Arm B Home based supported exercise
- Arm C Standard care, treatment as usual

Patients undergoing curative surgery for colorectal cancer are not routinely investigated with a CPET to assess cardiopulmonary fitness, or given any advice/support with respect to exercise prior to surgery.

All patients, once consented to the trial, will have a baseline CPET and another CPET immediately prior (within 7 days) of their planned colorectal surgery.

Data on planned type of surgery (laparoscopic or open) and tumour histological stage data at 30 days post-surgery will be collected and recorded on the relevant pages of the eCRF. If a patient is found to have had a benign tumour post-operatively, they may continue to participate in the study as per protocol.

If the patient is undergoing rectal cancer long course chemo-radiotherapy, this should be carried out before the patient is consented to the trial. There would then be a 6 week delay to their participation whilst they undergo chemo-radiotherapy. Once chemo-radiotherapy is complete, the patient will be approached for informed consent and a baseline assessments performed.

Patients will then receive, in addition to treatment as usual, the interventions below, depending on their treatment arm allocation during randomisation.

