5.7 Sample Size

An overall sample of 1146 patients (randomised 1:1:1) provides 90% power.

Post-operative complications are evident in 55% of patients by day 30 in patients receiving standard care. To detect a 25% reduction (relative risk 0.75) between standard care and each of the exercise groups (90% power, alpha 2.5%) 343 patients are required in each arm, giving 1029, 10% attrition rate - Total 1146. Average SF 36 score at 1 year is 52 SD 10.To detect a 3 unit difference between standard

care and each of the exercise groups (90% Power, alpha 2.5%) requires 276 in each arm, 3 arms 828, 20% attrition rate. Total 1035.

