5.10.4.6 Efficacy Analyses

The group comparisons which will be made are: a) TAU vs Hospital Based Supervised Exercise; b) TAU vs Home Based Supported Exercise; and c) Hospital Based Supervised Exercise vs Home Based Supported Exercise. The comparison a) and b) are the primary comparison and c) is an exploratory comparison as it is not possible to adequately power this comparison. No adjustment is made for multiple testing due to the number of groups as we are treating the comparisons a) and b) as separate research questions so we do not need to control the type 1 error/false positive rate.

For all 3 comparisons with the primary outcomes we will have a significance level of 2.5% to account for having two primary outcomes, this is based on the Bonferroni adjustment of dividing the significance level by the number of comparisons made for each research question. For all secondary outcomes the significance level will be 5%.

Within each group comparison for all continuous outcomes, a general linear model will be used to compare the average values between groups adjusted for the site as the randomisation is stratified by site. Depending on the number of individuals recruited at each site, site will be included as either a fixed or random effect. Assumptions will be checked graphically and if appropriate transformations will be used, if none are appropriate then a Bootstrap will be used. For binary outcomes a logistic regression model will be used adjusting for site.

In addition to the above analysis if any factor is imbalanced at baseline or is considered prognostic by discussion with the PI/TMG/DMC they will be included in an adjusted model. However, the primary analysis is the unadjusted analysis and the adjusted analysis exploratory.

If appropriate, that is to say that there is a large amount of non-adherers to the intervention, then a Complier Average Causal Effect (CACE) analysis will also be undertaken.

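### The primary 30-day morbidity model adjusts for site alone, and prognostic factors enter only an exploratory model with covariates not named in advance: a modest loss of efficiency and pre-specification

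*Protocol*

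**What the plan says.** The primary binary outcome is any morbidity, present or absent, at 30 days after operation (protocol 5.10.4.2). Section 5.10.4.6 fixes its model: "For binary outcomes a logistic regression model will be used adjusting for site". Site is also the only stratification factor (5.9.1.1).

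Section 5.10.4.6 then plans a further model. It would contain factors that turn out imbalanced at baseline, or that are judged prognostic after discussion with the PI, the management group or the monitoring committee. No factor is named and no time is set for that discussion. The ranking is explicit: "However, the primary analysis is the unadjusted analysis and the adjusted analysis exploratory".

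Three other places bear on which factors matter:

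- Section 4.1 reports a correlation between cardiopulmonary fitness and post-operative outcome, and 4.1.1 says that "CPET variables can reliably predict patients at increased risk of post-operative complications and morbidity following major surgery".
- Section 4.1 notes that a UK trial of open versus laparoscopic resection had a complication rate of only 34%. It says this may be due to "differences in the severity of the study population as EnROL required patients to be suitable for laparoscopic surgery".
- Section 5.4 says that planned surgery type, laparoscopic or open, is collected. It does not say clearly when, and Table 1 has no row for it.

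**The concern.** When a baseline factor predicts a binary outcome, a logistic model that includes it tests the arm effect with more power than one that leaves it out. The protocol itself says that fitness predicts complications and suggests that suitability for laparoscopy may do so. Neither can enter the headline analysis.

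The second issue is how the exploratory model is built. Choosing covariates because they look imbalanced, or by a discussion with no fixed date, lets the data shape the model. One of the bodies named, the monitoring committee, sees accumulating comparative data (5.11.4.4.4). If surgical approach were imbalanced by chance, the site-only result and the adjusted result could differ. The adjusted result would then have little standing, because its covariates were not fixed beforehand.

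**Working it through.** **Inputs from section 5.7.** "Post-operative complications are evident in 55% of patients by day 30 in patients receiving standard care", so the control risk is 0.55. "To detect a 25% reduction (relative risk 0.75) between standard care and each of the exercise groups" gives an exercise risk of 0.55 × 0.75 = 0.4125 and a difference of 0.1375. Alpha is 2.5%, power 90%, with 343 per arm and 10% attrition. Sidedness is not stated; two-sided is assumed because it reproduces the figure.

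**Reproducing the sample size.** With z(0.9875) = 2.2414, z(0.90) = 1.2816 and mean risk 0.48125:

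- n = [2.2414·√(2 × 0.48125 × 0.51875) + 1.2816·√(0.2475 + 0.2423)]² / 0.1375² = 325.5, so 326.
- With continuity correction: (325.5/4)·[1 + √(1 + 4/(325.5 × 0.1375))]² ≈ 340, within 1% of the stated 343.
- Attrition: 343/0.9 = 381.1, so 382 per arm, and 3 × 382 = 1146. This matches.
- Power of a two-proportion test at 343 per arm is 91.6%. The sample size does not rely on covariates.

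**Wald power of the logistic model without covariates, 343 per arm.**

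- Log odds ratio = logit(0.4125) − logit(0.55) = −0.5543 (odds ratio 0.574).
- SE = √[1/(343 × 0.2475) + 1/(343 × 0.2423)] = 0.1543.
- z = 0.5543/0.1543 = 3.592. Power = Φ(3.592 − 2.241) = 91.2%.

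**Adding surgical approach.** The protocol gives no complication risk by approach, so these control risks are assumptions, as is the 50:50 split. The conditional odds ratio is set so that overall risks stay at 55% and 41.25%. The SE comes from the information matrix of the model with arm and approach. Equivalent n is 343 × (3.592/z)², rounded up.

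| Control risk, laparoscopic/open | Conditional odds ratio | SE | z | Power | Equivalent n per arm |
|---|---|---|---|---|---|
| No adjustment | 0.574 | 0.1543 | 3.592 | 91.2% | 343 |
| 50% / 60% | 0.571 | 0.1551 | 3.610 | 91.4% | 340 |
| 45% / 65% | 0.561 | 0.1578 | 3.662 | 92.2% | 331 |
| 40% / 70% | 0.543 | 0.1624 | 3.755 | 93.5% | 314 |

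Before rounding, the gains are 0.3, 1.1 and 2.3 points.

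**A smaller effect.** At a relative risk of 0.80 (an assumption, not the design effect), power without covariates is 73.7%. The same three scenarios give 74.2%, 75.5% and 77.9%.

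**Site in the model, approach and fitness added.** These are 4,000 simulated trials per scenario with 20 sites assumed; simulation error is about 0.4 points.

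- No prognostic value: 91.6% site-only, 91.4% adjusted.
- Weak (50%/60%, fitness odds ratio 1.28 per SD): 92.6% to 93.3%.
- Moderate (45%/65%, fitness odds ratio 1.49 per SD): 92.8% to 94.2%.

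Adjustment costs almost nothing when the covariates are useless and gains about 0.7 to 1.5 points when they are weak to moderate.

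**The case against.** Adjusting the primary analysis for the sole stratification factor is a standard, valid choice. The trial reaches its stated power that way, and a covariate-adjusted model is already planned as support. All of this stands, and it limits the point to an improvement.

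Three stronger readings are tempting, and the protocol does not support them.

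- **A large gain from the protocol's own figures.** A reader might take 34% as the laparoscopic risk and, with a 50:50 split and 55% overall, back out 2 × 55 − 34 = 76% for open surgery. But the 34% is the total rate in a trial of both approaches among patients suitable for laparoscopy. The 55% comes from a separate series. Section 4.1 also says that rates vary with patient selection, follow-up and definition, and its remark on case mix is hedged. No risk by approach can be derived.
- **A biased primary result.** The site-only odds ratio lies slightly nearer 1 than the conditional one because odds ratios are non-collapsible. Under randomisation the marginal comparison, which is what the relative risk of 0.75 targets, remains valid.
- **A gain for free.** Collection of planned approach was added in version 4.0, dated 16.05.2017, after the first enrolment date of 1 November 2016. Patients may be randomised without CPET data (5.6.1.3). ASA I-III is an eligibility criterion, but the protocol does not say that the grade is recorded as data, nor does it link ASA to complications.

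What remains is that the protocol settles the matter itself. It puts the more efficient model in the exploratory tier and lets observed imbalance or undated discussion choose its covariates.

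**Conclusion.** The point holds as a weakness of efficiency and pre-specification. The primary analysis is valid and adequately powered under the protocol's assumptions. Adjusting for approach alone would add about 0.3 to 2.3 points of power at a relative risk of 0.75, equivalent to 340 to 314 patients per arm doing the work of 343. At a relative risk of 0.80 the gain would be about 0.5 to 4.2 points. These sizes rest on assumed risks by approach, a 50:50 split and complete covariate data; missing values would reduce them. The benefit that does not depend on those assumptions is a covariate set fixed before the data are seen.

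**What to change.** In section 5.10.4.6:

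1. Name a short list of pre-randomisation covariates for the primary 30-day morbidity model, in addition to site. These are planned surgical approach as intended at randomisation, and a baseline fitness measure or ASA grade where it is recorded. Use planned and not actual approach, and have it entered on the eCRF before allocation.
2. State a simple missing-covariate rule, such as a missing indicator or single imputation of baseline values. It should cover patients enrolled before planned approach was collected and those randomised without CPET. Say also how a baseline CPET done in the 7 days after randomisation, which 5.6.1.3 allows, is treated.
3. Report standardised risks with the risk ratio and risk difference, so that the result can be read against the 0.75 target.
4. Keep the site-only model as a sensitivity analysis, and delete the selection of covariates by observed imbalance.
5. Correct the word used for the primary analysis: it is called unadjusted although it adjusts for site.

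The cost is wording, one missing-data rule and a fixed time for recording planned approach. No new visit is needed. The small downsides are that the adjusted odds ratio is conditional, which item 3 deals with, and that some baseline values will be missing.
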